Drug use disorders commonly follow a history of experiencing high levels of early-life stress (ELS) (Repetti, Taylor et al. 2002, Dube, Felitti et al. 2003, McFarlane, Clark et al. 2005, Cohen, Paul et al. 2006), which have been linked with neural dysfunction (Cohen, Grieve et al. 2006, Seckfort, Paul et al. 2008, Baker, Williams et al. 2013, Philip, Sweet et al. 2013). HIV and high ELS have combined pathological effects on brain morphometry and neurocognitive function in HIV+ patients (Clark, Cohen et al. 2012). MA abuse and high ELS have some common effects, both involving upregulation of neuroinflammatory processes. High levels of ELS also are associated with increases in pro-inflammatory cytokines (Pollitt, Kaufman et al. 2007, Carpenter, Gawuga et al. 2010, Slopen, Lewis et al. 2010). These findings suggest that high ELS may exacerbate MA-related neuropathology in HIV+ patients and therefore we will explore potential effects of ELS on treatment outcomes as well as interactions with ibudilast treatment. As recent stress and/or trauma may confound any associations between ELS and neuroinflammation or cognition, we will assess recent stress and trauma using the Perceived Stress Scale (PSS-14) and the Posttraumatic Stress Disorder Checklist - Civilian (PCL-C) and control for these in our analyses.

Research Plan

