A high-value CM intervention adapted from (Bisaga, Aharonovich et al. 2010) will be used to characterize participants on their ability to achieve initial MA abstinence during the second week of the lead-in period, a potential confounder of subsequent medication effects. Participants will be instructed at the first study visit that they will have the chance to earn gift cards for providing MA-free urine drug screens during the second week of the lead-in period. Participants will receive \$15 for the first MA-free urine provided during the second week, \$25 for the second MA-free urine provided, and \$40 for the third MA-free urine provided. Participants will be advised that achieving initial MA abstinence during the lead-in may be beneficial to their eventual treatment outcomes, but that failure to achieve abstinence will not affect their subsequent participation and those unable to abstain will be encouraged to complete the screening in order to avoid differential attrition. Participants will be stratified in secondary analyses by their ability to achieve MA abstinence with the CM intervention during the two-week lead-in period. All participants will receive \$25 in gift cards upon completion of the screening measures, regardless of urine drug screen results, to compensate participants for time spent completing screening measures. Participants who complete all baseline/eligibility assessments and meet all eligibility criteria will be randomized and begin study treatments and medication within 1 week of completion of screening measures

Eligibility Requirements: Participants randomized into the study must meet the following eligibility requirements:

Inclusion criteria:

- (1) 18 years of age or older;
- (2) meet DSM-IV-TR criteria for MA dependence (SCID verified);
- (3) a MA-positive urine drug screen at one or more visit during the two week lead-in period;
- (4) seeking treatment for MA problems;
- (5) willing and able to comply with study procedures;
- (6) provide written informed consent;
- (7) English speaking;
- (8) live within 35 miles of the clinical research site; and
- (9) if female of childbearing potential, not pregnant or lactating and willing to use a medically reliable method of birth control during the trial (e.g., birth control pills, Depo-Provera, and/or condoms with spermicide).

Exclusion criteria:

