Concomitant Medications: All subjects will be asked about concomitant medications weekly during the lead-in and outpatient treatment period. Concomitant medications include both OTC and prescribed medications.

Early Life Stress Questionnaire (ELSQ): The Early Life Stress Questionnaire (McFarlane, Clark et al. 2005) (ELSQ) is a self-report questionnaire that considers 19 adverse life events (crime, sexual abuse, family conflict, bullying, etc.). High ELS is defined as exposure to ≥ 3 ELS events prior to age 19 (Cohen, Paul et al. 2006, Paul, Henry et al. 2008, Seckfort, Paul et al. 2008, Clark, Cohen et al. 2012), consistent with the rates of ELS in the general population (Cohen, Paul et al. 2006). Previous studies (Cohen, Grieve et al. 2006, Cohen, Paul et al. 2006, Seckfort, Paul et al. 2008, Clark, Cohen et al. 2012) have shown that using a cut-point of ≥ 3 ELS events provides the greatest discrimination on the basis of ELS for behavioral and neural measures. The ELSQ will be administered during week 3.

Perceived Stress Scale (PSS-14): The PSS-14 is a validated, self-report questionnaire that assesses the extent to which individuals perceive their life to be stressful (Cohen and Williamson 1988). The PSS-14 will be administered during baseline.

Posttraumatic Stress Disorder Checklist - Civilian version (PLC-C): is the most commonly used self-report questionnaire assessing number and severity of PTSD symptoms. The PLC-C will be administered during week 3.

Genotyping/SNP: 10 ml whole blood will be collected at baseline for DNA extraction for genotyping analyses.

Hamilton Depression Rating Scale (HAMD) (Riskind, Beck et al. 1987): Completed in just 5 to 10 minutes, the HAMD can be used to quickly evaluate symptom severity, to confirm a diagnosis of depression, to explore depressive symptoms, and to measure treatment outcome. The HAMD will be administered during the lead-in period and weekly during the medication and follow-up phase.

HIV CD4 Count and Viral Load: Participants who are HIV+ will have CD4 count and viral load measured at baseline, at the termination of medication (week 13), and at the last follow-up visit (week 16).

HIV medication adherence: Participants who are HIV positive will have their HIV medication adherence assessed monthly by asking them to estimate the proportion of their medications that they took in the past month.

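### Controlling for current stress and PTSD symptoms can remove part of the early-life-stress association, so the adjusted model should not stand alone

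*Combined protocol and SAP*

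**What the plan says.** The last paragraph of the Background introduces ELS as something that may worsen methamphetamine-related neuropathology. It announces an exploration of ELS effects on treatment outcomes and of interactions with ibudilast. It then gives the reason for two further scales, "As recent stress and/or trauma may confound any associations between ELS and neuroinflammation or cognition, we will assess recent stress and trauma", names the PSS-14 and the PCL-C, and commits to use them "and control for these in our analyses".

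Study Measures and Assessments describes the three instruments:

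- **ELSQ:** a self-report list of 19 kinds of adverse event, sexual abuse and bullying among them. High ELS means "exposure to ≥ 3 ELS events prior to age 19". It is given in week 3 of medication.
- **PSS-14:** a self-report scale that "assesses the extent to which individuals perceive their life to be stressful". On timing: "The PSS-14 will be administered during baseline".
- **PTSD checklist** (spelled PLC-C there): it "is the most commonly used self-report questionnaire assessing number and severity of PTSD symptoms". It is also given in week 3.

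The Exploratory analyses paragraph under Data Analysis plans correlations of ELS with baseline methamphetamine severity and with treatment outcomes, plus ELS-by-ibudilast interactions. It names no covariates for these. It does not list the ELS associations with inflammation or cognition, so the Background sentence is the only analysis rule for them.

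**The concern.** A confounder of ELS and a later marker is something that influences both, or that stands in for such a cause. The plan treats current stress and PTSD symptoms in that way. Yet the exposure is a set of childhood and adolescent events, and the covariates describe the participant's state at enrolment or three weeks into treatment. Perceived stress and PTSD symptoms in adulthood are plausible results of such events. The checklist, as described, does not separate symptoms of recent trauma from symptoms left by the ELS events themselves.

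If the covariates are results of ELS, a model containing them estimates only the part of the association that does not run through them. The plan does not say whether the total association or the part net of current stress is wanted. It does not mention mediation, and it schedules no estimate without the two scales for inflammation or cognition. In exploratory, unpowered analyses meant to inform later trials, a shrunken coefficient could be read as showing that ELS does not matter.

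**Working it through.** The plan gives no effect size, correlation or power for the ELS analyses, so there is no figure to reproduce. The check is of time order and content first, then of what adjustment does under stated assumptions.

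**1. Time order.** High ELS is counted from events before age 19. Participants are "18 years of age or older", so the exposure window is closed at entry, or within a year of closing for an 18-year-old. The PSS-14 is taken at baseline and the checklist in week 3. Both covariates therefore follow the exposure, apart from that small overlap.

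**2. Content.** The Background presents the two scales as measures of recent stress and trauma. The instrument entries describe perceived stress and PTSD symptoms. No restriction to recent trauma is stated for the checklist.

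**3. If the covariates are consequences of ELS.** Scale ELS and current stress to unit variance. Let a be the path from ELS to current stress, b the path from current stress to the marker, and c the direct path. Then:

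- total association = c + a×b
- association adjusted for current stress = c
- share removed = a×b / (c + a×b)

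All path values are assumptions: a from 0.2 to 0.5, b from 0.1 to 0.3, c from 0.1 to 0.3, and the special case a = 0.

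| Case | c | a | b | Total | Adjusted | Removed |
|---|---|---|---|---|---|---|
| No ELS-to-stress path | 0.2 | 0 | 0.2 | 0.20 | 0.20 | 0% |
| Smallest non-zero | 0.3 | 0.2 | 0.1 | 0.32 | 0.30 | 0.02/0.32 = 6% |
| Middle | 0.2 | 0.35 | 0.2 | 0.27 | 0.20 | 0.07/0.27 = 26% |
| Largest | 0.1 | 0.5 | 0.3 | 0.25 | 0.10 | 0.15/0.25 = 60% |

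A simulation of the middle case with one million subjects gave 0.271 unadjusted and 0.200 adjusted, as the algebra predicts.

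**4. If an unmeasured factor also drives both current stress and the marker**, with path u to each, the adjusted coefficient becomes c − a×u²/(1 − a²). In the middle case, 1 − a² = 0.8775:

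- u = 0.3: 0.20 − 0.35×0.09/0.8775 = 0.164 (simulated 0.165)
- u = 0.5: 0.20 − 0.35×0.25/0.8775 = 0.100 (simulated 0.098)

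The unadjusted estimate stays at about 0.27. The adjusted model is then not a clean direct effect either.

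**5. The opposite case.** Suppose an earlier cause raises both ELS and current stress, with path 0.5 to each, and ELS does not affect current stress. The two then correlate 0.5×0.5 = 0.25. With a true ELS effect of 0.20 and a stress effect of 0.20, the unadjusted coefficient is 0.20 + 0.20×0.25 = 0.25. The adjusted one is 0.20 (simulated 0.201). Here adjustment gives the right answer.

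**6. Correlations alone do not decide between steps 3 and 5.** The two-predictor formula is (r_EM − r_EP×r_PM)/(1 − r_EP²), with E for ELS, P for PTSD symptoms and M for the marker. Assume r_EM = 0.20 and r_PM = 0.30:

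- r_EP = 0.3: (0.20 − 0.09)/0.91 = 0.121, a drop of 40%
- r_EP = 0.4: (0.20 − 0.12)/0.84 = 0.095, a drop of 52%
- r_EP = 0.5: (0.20 − 0.15)/0.75 = 0.067, a drop of 67%

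The formula contains no information on causal direction.

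**The case against.** The strongest objection is that time order does not settle the matter. A reader might infer that adult stress cannot confound, because it cannot cause events before age 19. That does not follow for the exposure as measured. The ELSQ is a retrospective self-report given in the same week as the PTSD checklist, and current distress can affect what is recalled and reported. A covariate also need not cause the exposure to be useful; it can stand in for a shared earlier cause, as in step 5. Both points stand, although the documents offer neither as the reason for adjusting.

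A second objection is that the association net of current stress is a legitimate target, and that the Background can be read as wanting it. This also stands. What is missing is a statement of the target.

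A third concerns size. A reader might take the 40% to 67% drops in step 6 as the amount lost. The documents do not support that: every correlation is assumed, and if the covariates act as confounders the same drop is bias being removed.

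A fourth concerns scope. The stated rationale covers neuroinflammation and cognition. The correlations with methamphetamine severity and treatment outcomes are planned without named covariates, so it should not be assumed that they are adjusted.

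None of this answers the narrower point that a single adjusted estimate, presented as corrected for confounding, cannot show which situation holds.

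**Conclusion.** The point holds in a limited form. The plan states that it will control for two variables that, by its own description, can be consequences of the exposure. Adjustment can then remove part of the total ELS association with inflammatory markers and cognition. The documents do not allow the amount to be estimated: it is zero if ELS does not affect current stress, and the 6% to 60% range is an illustration that rests wholly on assumed paths in a linear model.

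It would go too far to say that the two scales do lie on the causal path, or that adjustment is wrong; the documents contain no data on either. The analyses are declared exploratory and unpowered, and the sample size, the primary outcome and the randomised drug comparison are untouched. This is a cheap improvement.

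**What to change.** Amend the early-life-stress paragraph of the Background and the Exploratory analyses paragraph so that each ELS association with inflammatory markers and with cognition is reported twice:

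1. **Without PSS-14 and PCL-C**, adjusting only for factors that precede ELS or cannot result from it, such as age and gender. HIV status should not be included by default. The Background says that drug use disorders commonly follow high ELS and that HIV incidence is higher among men who have sex with men who use methamphetamine, so HIV status may itself be a later result of ELS.
2. **With PSS-14 and PCL-C**, labelled as the association not explained by current stress or PTSD symptoms.

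The same text should say whether the adjustment is meant to reach the correlations with methamphetamine severity and treatment outcomes. If it is, the same pair of models applies there. Reporting both does not require the causal question to be settled, and the sponsor's confounding view remains visible in the second model.

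The cost is one sentence and one extra model per exploratory analysis, with no new data.

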The study is a phase 2 clinical trial to determine the safety and efficacy of IBUD for the treatment of MA dependence. The trial will be performed at the UCLA outpatient research clinic in Hollywood, California. Treatment-seeking MA dependent volunteers will undergo screening and eligibility assessments, including determination of HIV serostatus, during a two-week placebo lead-in with a high value contingency management (CM) behavioral intervention aimed at assessing participants' ability to adhere to medication taking and initiate MA abstinence prior to the start of medication, both important predictors of subsequent treatment outcomes (Bisaga, Aharonovich et al. 2005, Anderson, Reid et al. 2009, Bisaga, Aharonovich et al. 2010). Eligible participants (N = 140) will be randomized, stratified by HIV serostatus, to IBUD (50 mg BID) or placebo (BID) treatment for 12 weeks, with twice weekly clinic visits for counseling, urine drug tests, and safety/medication adherence monitoring (Figure 4). An urn randomization procedure will be used to balance the following variables between active and placebo groups: MA use during the two-week placebo/CM lead-in period, gender, ethnicity (Hispanic versus not Hispanic), marijuana dependence, and baseline cognitive function.

Figure 4: Study Schema

The study is powered to detect a statistically significant benefit of IBUD over placebo on the primary study outcome, MA abstinence during the final two weeks of treatment (at least one of the two possible urine drug screens each week is available during weeks 11 and 12 and all available samples are MA negative, the FDA-preferred primary efficacy outcome for phase 2 stimulant trials) in the total sample (N = 140). Treatment retention for participants receiving IBUD versus placebo will also be compared.

Secondary analyses will examine medication tolerability and adverse events, as well as treatment outcomes in pre-specified subgroups defined by level of medication adherence, the ability to achieve initial MA abstinence during the placebo/CM lead-in, and baseline HIV serostatus. Exploratory analyses aimed at probing the mechanism of action for IBUD in MA dependence will examine potential associations between treatment outcomes/medication effects and a panel of inflammatory and neurotrophic markers as well as polymorphisms in dopaminergic and GDNF genes.

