The study clinician may reduce a participant's dose from 100 mg/day to 80 mg/day (40 mg in AM and 40 mg in PM), or potentially 30 mg BID, for any potential dose-related side effects but dose increases will not be allowed. The study physician may temporarily discontinue (hold) study medication for up to two weeks followed by re-initiation of study medication in the event of transient adverse events but if the medication is not re-started within two weeks of holding, the medication will be discontinued. If the medication is discontinued, medication adherence checks and compensation will be discontinued as well. Urine samples will be collected for UV fluorimetry and storage up to 1 week post-medication discontinuation. MM counseling will continue through the remaining study weeks (up to week 12) to support and monitor the participant.

Data and Safety Monitoring Board (DSMB) and Trial Stopping Rules: A Data and Safety Monitoring Plan will be submitted to NIDA and the UCLA Addiction Medicine DSMB and approved prior to enrolling participants. The UCLA Addiction Medicine DSMB will monitor the study and review study progress and adverse events after the first 35 participants have been enrolled and then at least yearly. Any SAEs that occur will be reported to the DSMB, as well as all other regulatory bodies monitoring the trial (e.g. FDA, NIDA, UCLA IRB) at the time of the occurrence of the SAE. In addition, an interim blinded group analysis will be performed once mid-way through the trial when approximately half of the proposed 140 individuals have been enrolled. At this time, the person responsible for randomization will confirm that randomization is proceeding according to the protocol.

While statistical guidelines for stopping the trial are provided below, they are intended as a guide for the DSMB and other regulatory bodies to use in making a determination as to whether the trial should be stopped or continued and will not in isolation trigger discontinuation of the trial. The following statistical guidelines are provided for consideration of stopping the trial:

- If the frequency of SAEs is statistically significantly greater ($p < 0.05$) in the IBUD group compared to the placebo group at interim analysis or anytime during the trial, consider stopping the trial.

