During weeks 4 and 13, participants will repeat the following tasks: Montreal Cognitive Assessment; MATRICS CPT-II; HVLIT-R; BVMT-R; SST; TMT; DDT; WAIS-IV Letter Number Sequencing ; WAIS-IV Symbol Search, WAIS-IV Digit Symbol Coding; N-Back Task; DKEFS Color Word Interference and the Iowa Gambling Task.

Data Analysis: The primary objective of this study is to determine the efficacy of IBUD as a treatment for MA dependence and to provide FDA with sufficient data to advise whether IBUD should move forward for marketing as a MA dependence treatment. The primary outcome variable is the FDA-specified criterion of significant MA abstinence at the end of treatment defined as no self-reported MA use during the final two weeks of treatment (weeks 11/12) confirmed via urine drug screens (at least one of the two possible urine specimens each week is available during weeks 11 and 12 and all available urine specimens are MA-negative). The study is powered to detect a significant difference in the proportion of participants achieving this outcome in the IBUD versus placebo groups. Additional measures of clinically meaningful reductions in MA use during treatment will also be assessed in the event that IBUD produces effects on MA use that do not meet the abstinent at end of treatment threshold. In addition to MA use outcomes, treatment retention, an important clinical variable that is associated with long-term treatment outcomes in substance abuse treatment (Hser, Evans et al. 2004), with IBUD versus placebo will be compared. Effects of potential confounders on each of these outcomes will also be examined including: (1) medication non-adherence, (2) medication safety and tolerability (adverse event rates), and (3) ability to achieve initial MA abstinence with the CM intervention during the two week lead-in period.

A general univariate strategy will be used to test for differences between conditions at baseline and along all outcome variables using bivariate analyses (i.e., t-tests/ANOVA for continuous variables; χ^2 for dichotomous variables). A multivariate analysis will also be used when appropriate to control for co-variables known to influence MA dependence treatment outcomes including age, gender, baseline severity of MA dependence, HIV status, and ability to achieve initial abstinence during the CM lead-in.

Aim 1: To determine whether IBUD reduces MA use more than placebo among MA dependent participants.

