Examination of potential confounders Rates of adverse events and medication adherence in the IBUD and placebo groups will be calculated and compared. Medication adherence will be assessed as a continuous variable: the proportion of twice-weekly urine drug samples positive for riboflavin (≥ 900 ng/ml riboflavin as determined via quantitative fluorimetry), and as a dichotomous variable: medication adherent ($\geq 80\%$ of twice-weekly urine drug screens positive for riboflavin). Adherence will also be assessed via qualitative measurement of IBUD and metabolites in urine and serum samples, which is the gold standard for assessing adherence in the IBUD group but is limited by the fact that assessment of adherence in the placebo group is not possible. Models for MA use outcomes will be repeated including the continuous measure of adherence as a co-variate. The models will also be run with the sample stratified as medication adherent versus non-adherent. As pre-treatment abstinence is an important predictor of treatment outcomes and medication response in stimulant dependence trials (Elkashef, Rawson et al. 2008, Bisaga, Aharonovich et al. 2010), the sample will be stratified by ability to achieve initial abstinence with CM during the two-week lead-in period to explore whether medication effects may differ in these subgroups.

Aim 2: To determine whether IBUD results in longer treatment retention than placebo among MA dependent participants.

Hypothesis 2: IBUD will result in significantly greater treatment retention than placebo

Analysis: The mean number of days retained, defined as the number of days from the start of study medication to the final clinic visit during the 12 week treatment period, will be compared for IBUD versus placebo via t-test. Cox proportional hazards model will be used to compare days retained for IBUD versus placebo controlling for co-variables including age, gender, and baseline MA use. These analyses will then be repeated with the sample stratified by ability to achieve initial abstinence with CM during the two-week lead-in period to explore whether medication effects may differ in these subgroups.

The following exploratory HIV-related aims will be address in the HIV positive participants.

Aim 3: To determine whether IBUD improves biological (CD4 count; HIV RNA) and neurocognitive outcomes more than placebo among HIV-positive MA dependent participants.

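### Adverse event rates are to be compared between arms with no denominator defined and default tests that ignore time observed, although the plan expects high attrition and longer retention on IBUD

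*Combined protocol and SAP*

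**What the plan says.** Safety is a stated objective next to efficacy. The text on how it is compared is short:

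- Research Plan: "Secondary analyses will examine medication tolerability and adverse events, as well as treatment outcomes in pre-specified subgroups".
- Data Analysis, Examination of potential confounders: "Rates of adverse events and medication adherence in the IBUD and placebo groups will be calculated and compared". Numerator, denominator, observation window and test are not given.
- Data Analysis, opening paragraphs: "A general univariate strategy will be used to test for differences between conditions at baseline and along all outcome variables using bivariate analyses", with t-tests/ANOVA for continuous variables and chi-square for dichotomous ones. Multivariate analysis is added where appropriate.
- DSMB and Trial Stopping Rules: the first guideline begins "If the frequency of SAEs is statistically significantly greater ($p < 0.05$) in the IBUD group compared to the placebo group". Neither test nor denominator is stated. The section adds that the guidelines alone will not stop the trial.

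On time observed:

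- The Drop-out Subject Tracking section expects attrition to be high. It plans weekly contact with drop-outs who have not withdrawn consent, to complete the weekly data.
- Under Aim 2 the hypothesis is that "IBUD will result in significantly greater treatment retention than placebo". Time on study is defined there: "The mean number of days retained, defined as the number of days from the start of study medication to the final clinic visit". It is used for the retention analysis only.
- AEs are assessed at screening, weekly in the medication phase and at follow-up (Study Measures and Assessments; Appendix II).

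**The concern.** A participant seen for longer has more chance to report an AE. If the arms differ in time observed, the proportion with an AE and the mean number of AEs will differ even when the weekly risk is the same. The plan predicts such a difference in its own second hypothesis, and handles time properly for retention (a Cox model for days retained) but not for AEs.

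The bias can run either way. If IBUD improves retention and is harmless, a crude comparison tilts towards an excess of AEs on IBUD. If IBUD is poorly tolerated and people leave early, it tilts towards reassurance. Leaving the denominator open also means that it could be chosen after the data are seen, and the choice can change the safety conclusion.

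**Working it through.** The plan states no AE rate, retention rate or safety power, so it has no figure of its own to reproduce. From the documents: 70 per arm and a 12-week medication phase. Assumed: all retention values and AE hazards, and, unless stated otherwise, no AE observation after drop-out.

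**Step 1. Time observed.** With exponential drop-out and a fraction r retained at 12 weeks, μ = −ln(r)/12 and mean weeks observed = (1 − r)/μ.

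- r = 0.50: μ = 0.0578; 0.50/0.0578 ≈ 8.66 weeks
- r = 0.60: μ = 0.0426; 0.40/0.0426 ≈ 9.40 weeks
- r = 0.70: μ = 0.0297; 0.30/0.0297 ≈ 10.09 weeks

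With a true rate ratio of 1, the crude ratio of AE counts is 9.40/8.66 = 1.09 (60% v 50% retained) or 10.09/8.66 = 1.17 (70% v 50%). If IBUD retains 50% and placebo 70%, it is 8.66/10.09 = 0.86.

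**Step 2. Proportion with any AE.** With weekly hazard λ, P = λ/(λ + μ) × [1 − exp(−12(λ + μ))]. For λ = 0.1:

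- 50% retained: 0.1/0.1578 × (1 − e^−1.893) = 0.538
- 70% retained: 0.1/0.1297 × (1 − e^−1.557) = 0.608

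The ratio is 1.13. Over λ = 0.005 to 0.3 the inflation is 4–8% at 60% v 50% and 8–16% at 70% v 50%, larger for rarer events. If AEs fall only in the first two weeks, it is 1–4% (IBUD retention 60–80% v placebo 50%).

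**Step 3. False-signal rates (simulation, equal true hazard).** One-sided Fisher test on any AE, nominal 5%, λ = 0.1–0.3: about 9% at 60% v 50% retained and 16–21% at 70% v 50%. A person-time comparison gives 4–5%.

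T-test or chi-square, nominal 2.5% in the direction of IBUD worse, with gamma variation in risk between people:

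| Setting | False finding that IBUD is worse |
|---|---|
| 9 v 8 mean weeks, λ 0.03–0.5 | 5–9% |
| 10 v 8 mean weeks, λ 0.03–0.3 | about 8–21% |
| 10 v 8, half of drop-outs tracked to week 12 | about 6–9% |
| 10 v 8, AEs only in weeks 1–2 | near nominal |
| 10 v 8, SAE-like events (λ = 0.005) | 3–4% |

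The 10 v 8 case is a large gap. Solving (1 − r)/μ for those means gives μ = 0.0314 and 0.0729, so r = e^(−0.376) = 0.69 and e^(−0.874) = 0.42.

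**Step 4. Candidate remedies.** At 10 v 8 weeks, with AEs confined to weeks 1–2 and equal true risk, events per person-week gave 5–10% false findings that IBUD is *better*, and roughly halved power for a true early excess. Under constant hazards its false-signal rate stayed near nominal. Time to first event stayed at 2–3% in every setting tried.

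**The case against.** Several points on the other side stand.

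- A reader might infer that the plan prescribes an unadjusted comparison. It does not: the word for rate is left undefined, and an exposure-based rate is neither specified nor ruled out. Nor are t-tests and chi-square the only methods named. Logistic regression, GEE, Cox and linear models appear for other outcomes, though none is tied to AEs. What remains is an undefined quantity with defaults that ignore time.
- Observation does not simply end at drop-out. Drop-outs who keep consent are to be met weekly, early terminators are asked to attend follow-up visits, and after study drug is discontinued the counselling visits, which ask about side effects, continue up to week 12. If carried out, this shrinks the bias. It does not remove it: withdrawn consent is not covered, tracking will be incomplete, and time on drug still differs. No rule says how AEs after drug stop are counted.
- A reader might infer that the SAE guideline could stop a safe trial. The calculations do not support that. At about 4–5% of participants with an event per arm, one-sided Fisher's test gives 2–2.5% at 60–70% v 50% retained, below its nominal 5%, and the guideline is advisory.
- Early onset is plausible, since the Dose Justification section titrates over the first days to limit nausea. This weakens the concern and counts against a person-week rate as the main analysis.

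**Conclusion.** The point holds as a gap in specification with a conditional bias. The AE rate has no denominator, the default tests ignore time observed, and the plan itself predicts unequal retention. If retention differs and AEs occur throughout treatment, the crude comparison can mislead in either direction.

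It would go too far to say that IBUD *will* look less safe. That needs a material retention gap, AEs spread over the 12 weeks and little observation after drop-out. The documents fix none of these, and every retention and hazard value used here is an assumption. The range runs from near nominal (early AEs) to about 21% against 2.5% (common AEs, a wide retention gap, no tracking). For the SAE guideline the issue is mainly an unnamed test and denominator. Overall this is a cheap improvement, not a flaw that undermines the trial.

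**What to change.** In the Data Analysis section, where AE rates are compared:

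1. Compare AEs between arms by time to first event from first dose: Kaplan-Meier with log-rank or Cox, censored at the last AE assessment. The documents do not say that onset dates are recorded. If they are not, use the week of the weekly AE assessment.
2. Show the simple proportions by arm alongside. Give events per person-week as a descriptive supplement only, because it assumes a constant hazard.
3. Report events on study drug separately from those collected after drug stop or drop-out.
4. For the SAE guideline, show person-weeks observed by arm beside the SAE counts, and name the test.

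The cost is SAP wording and one more AE summary. No new visits are needed, since AEs are already assessed weekly. One limitation remains: if people leave because of poor tolerability, censoring is informative and time to first event does not fully correct for it.
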